**Figure 1: Study Design**

#### **4.1.1. Options for the Open-Label Treatment Phase**

Subjects originally randomized to ruxolitinib with anagrelide placebo (Group A) who are receiving benefit from therapy can 1) continue receiving open-label ruxolitinib until the study is concluded or they meet discontinuation criteria, or 2) choose to discontinue therapy.

Subjects originally randomized to receive anagrelide plus ruxolitinib placebo (Group B) have 3 options: 1) they may cross over to begin receiving ruxolitinib if they meet eligibility criteria after consultation with the sponsor and may then continue until the study is concluded or they meet discontinuation criteria; 2) they may continue receiving anagrelide until the study is concluded or they meet discontinuation criteria; or 3) they can choose to discontinue therapy. Note that subjects originally randomized to Group B may cross over to receive ruxolitinib at any time during the open-label part of the study.

Subjects who will continue with the same active agent to which they were randomized will have a study visit at Week 56, at which time study drugs will switch over to open-label supplies (ruxolitinib or anagrelide) and then study visits every 12 weeks (Week 68, 80, etc). Subjects who were originally randomized to anagrelide (Group B) and who cross over to ruxolitinib will begin receiving ruxolitinib at the Week 56 visit. These subjects will have study visits at Weeks 1, 2, 3, 4, and every 4 weeks up to 52 weeks, then every 12 weeks thereafter. Subjects who initially remain on anagrelide after unblinding but choose to cross over to receive ruxolitinib at a later time will have study visits at Weeks 1, 2, 3, 4, and every 4 weeks up to 52 weeks, then every 12 weeks thereafter.

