#### 4.5. Overall Study Duration

The study begins when the first subject signs the ICF. The blinded treatment phase is complete and study data analysis can occur for the primary endpoint when all subjects have completed Week 52 or discontinued, and all study data through the Week 52 visit have been entered and the data cleaned and verified. The database will be frozen at this time for the initial data analysis to occur.

The study is completed when the last subject has reached Week 156 (approximately 3 years of treatment). Individual subject participation is expected to average 24 to 36 months.

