**Table 4: Schedule of Laboratory Assessments**

[figure not shown]
	Section	Screening Days -35 to -8	Baseline Days -7 to -1	Blinded Treatment (All Subjects)						Open-Label Treatment		EOT	Safety Follow-Up 30-37d After Last Dose	Notes
										Subjects Who Do Not Cross Over	Subjects Who Cross Over			
				W1-W3			W4- W52 q4w	W34-W50 q4w (lab only)		W56+ q12w	W56+ q12w			
				D1	D8 (±2d)	D15 (± 2d)	D22 (± 2d)	D7 (± 3d)	D7 (± 3d)	D7 (± 7d)	D7 (± 7d)			
Local laboratory assessments											See Table 6			
Hematology	7.5.6	X	X*	X*	X	X	X	X**	X**	X		X	X	* Should be taken as close as possible to Day 1 but may be drawn up to 3 days before first dose. Only 1 sample for baseline/Day 1 is required. ** Weeks 32-52 are evaluation period for primary endpoint: Should ALL be carefully monitored by sites.
Ferritin level	7.5.6		X											
Coagulation panel	7.5.6	X	X*	X*								X		* Should be taken as close as possible to Day 1 but may be drawn up to 3 days before first dose. Only 1 sample for baseline/Day 1 is required.
Serum chemistries	7.5.6	X	X*	X*	X	X	X	X		X		X	X	* Should be taken as close as possible to Day 1 but may be drawn up to 3 days before first dose. Only 1 sample for baseline/Day 1 is required.
Urine pregnancy test	7.5.6.1			X				X		X				Females of childbearing potential. Test should be repeated if required by local regulations. Not needed if FSH elevated or amenorrheic > 1 year.

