## **6.6. Safety Follow-Up**

The safety follow-up period is the interval between the EOT visit and the scheduled follow-up visit, which should occur 30 to 37 days after the EOT visit (or after the last dose of study

treatment if the EOT visit was not performed). Adverse events and SAEs must be reported up until 30 days after the last dose of study treatment, the date of the follow-up visit, or until study treatment-related toxicities resolve, return to baseline, or are deemed irreversible, whichever is longer. Reasonable efforts should be made to have the subject return for the follow-up visit and report any AEs that may occur during this period. If the subject cannot return to the site for the safety follow-up visit (eg, lives far away), then the subject should be contacted by telephone for assessing AEs and SAEs. Sites should be instructed to document this contact in the source.

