### 7.2.3.1.1. Primary Endpoint Status Determination

The primary efficacy endpoint is the proportion of subjects who achieve a simultaneous reduction of platelet counts to  $< 600 \times 10^9/L$  and of WBC counts to  $< 10 \times 10^9/L$  for at least 80% (6 out of 7 consecutive visits) of biweekly assessments for 12 consecutive weeks between Week 32 and Week 52. There are 5 consecutive 12-week periods: Weeks 32 to 44, Weeks 34 to 46, Weeks 36 to 48, Weeks 38 to 50 and Weeks 40 to 52.

For each of the 5 consecutive 12-week periods, 7 scheduled biweekly visits are planned. A subject will be flagged as "Responder," "Nonresponder," or "Nondeterminable" as the following at each period:

- If a subject has  $\geq 6$  visits with platelet counts  $< 600 \times 10^9/L$  and WBC counts  $< 10 \times 10^9/L$ , then this subject is flagged as Responder at this period.
- If a subject has  $\geq 2$  visits with platelet count  $\geq 600 \times 10^9/L$  or WBC counts  $\geq 10 \times 10^9/L$ , then this subject is flagged as Nonresponder at this period.
- If the above 2 conditions are not met for a subject, then this subject is flagged as nondeterminable at this period.
- If a subject discontinued from the study treatment between Weeks 32 and 52, the response status for the periods after the treatment discontinuation will not be assessed.

The primary endpoint status for a subject can be determined as the following:

- If any period is deemed as Responder for a subject, then the primary endpoint status of this subject is Responder.
- If "Nonresponder" is flagged in all assessed periods for a subject, then the primary endpoint status of this subject is Nonresponder.
- Otherwise, the primary endpoint status for a subject cannot be determined and the value will be missing.

If a subject discontinued from the study treatment before Week 32, then the primary endpoint status of this subject is missing.

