### 7.2.3.1.3. Covariates

Based on the clinical judgment ([Daly 2011](#), [Carel and Eviatar 1985](#)), the following covariates that may be related to the primary endpoint status will be considered:

- JAK2V617F mutation status at baseline: positive versus negative.
- Prior anagrelide use at baseline: yes versus no.
- Platelet count at baseline:  $\geq 1000 \times 10^9/L$  versus  $< 1000 \times 10^9/L$ .
- Last nonmissing assessment of platelet counts.
- Last nonmissing assessment of WBC counts.
- Last nonmissing assessment of hemoglobin.
- Any infection: yes versus no.
  - For subjects discontinued from the treatment before Week 32, any infection in the study period is considered; for subjects still in the study after Week 32, any infection after Week 32 is considered.
- Any trauma or surgery: yes versus no.
  - For subjects discontinued from the treatment before Week 32, any trauma or surgery in the study period is considered; for subjects still in the study after Week 32, any trauma or surgery after Week 32 is considered.

The covariates will be assessed based on data availability.

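### The SAP's only specified missing-data check on the primary endpoint uses predictors that mean different things in early stoppers and in the subjects it is fitted on, and no tipping-point analysis backs it up

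*SAP*

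**What the plan says.** The primary analysis (SAP 7.2.1) counts subjects who stop treatment without meeting the response criteria as nonresponders. SAP 7.2.3.1 adds a sensitivity analysis if more than 10% of subjects have missing primary status. In that analysis a subject is a responder or nonresponder only on the strength of biweekly counts between Weeks 32 and 52. For early stoppers, 7.2.3.1.1 says: "If a subject discontinued from the study treatment before Week 32, then the primary endpoint status of this subject is missing".

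Missing statuses are filled by logistic multiple imputation with m=5 (7.2.3.1.4), using treatment and the covariates of 7.2.3.1.3. On infection that section says "For subjects discontinued from the treatment before Week 32, any infection in the study period is considered", but "for subjects still in the study after Week 32, any infection after Week 32 is considered". Trauma or surgery is split in the same way. Three laboratory predictors are defined only as the latest available value, for example "Last nonmissing assessment of platelet counts", with no cut-off.

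The protocol schedules blood counts outside blinded treatment. The hematology row of Table 4 is marked in the column "Safety Follow-Up 30-37d After Last Dose". Section 6.6 counts from a different date: "scheduled follow-up visit, which should occur 30 to 37 days after the EOT visit". Group B subjects who "cross over to ruxolitinib will begin receiving ruxolitinib at the Week 56 visit" (4.1.1) have open-label counts from then on. These can exist at the time of analysis, because "study data analysis can occur for the primary endpoint when all subjects have completed Week 52 or discontinued" (4.5).

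Section 7.2.3.1.4 allows further imputation methods to be explored but names none.

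**The concern.** An imputation model carries a relation learned in one group over to another. That works only if a predictor has the same meaning in both. Here infection in the fitting set is infection at or after the endpoint window, when it may itself raise the WBC count being judged. In an early stopper it is infection at any time in a different and usually shorter period. The last counts in the fitting set usually fall in or after the endpoint window. In an early stopper they predate it, and read literally they may be taken off drug.

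This is the only specified analysis aimed at missing primary-endpoint data; the per-protocol and JAK2-status analyses in 7.2.3 address other questions. If it is unreliable, a weaker imputed result could be misread as fragility and an unchanged one would say little. Nor does it show what pattern of outcomes among the missing subjects would overturn the conclusion.

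**Working it through.** **1. The plan's own figures.** SAP 3.3 gives 30% vs 5%, 60 per arm and about 90% power. The pooled formula gives z = (0.25 − 1.96·√(2·0.175·0.825/60)) / √((0.30·0.70 + 0.05·0.95)/60) = (0.25 − 0.136)/0.0655 = 1.74, a power of 95.9%. The stated 90% is therefore not reproduced without an unstated allowance. If 20% of each arm stop and count as nonresponders, the rates become 24% vs 4% and power is 89.4%. Nothing below depends on this. Expected responders are 0.30·60 = 18 and 0.05·60 = 3. The check is triggered above 0.10·120 = 12 missing subjects, that is, at 13 or more.

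**2. Predictors side by side.**

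| Predictor | Known status (model fitted) | Stopped before Week 32 (imputed) |
|---|---|---|
| Infection; trauma/surgery | After Week 32 only, no end date stated | The study period |
| Last platelets, WBC, hemoglobin | Usually in or after Weeks 32–52; may be open-label, or after crossover from Week 56 | Before the window if on treatment; otherwise the end-of-treatment sample (within 7 days of last dose, Protocol 6.5) or the safety follow-up sample |

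The follow-up sample falls 30–37 days after the last dose by Table 4, or up to 37 + 7 = 44 days by Section 6.6. Either way the count is off treatment.

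**3. What a tipping-point table would show.** Let a and b be the responders per 60 on ruxolitinib and anagrelide, after some missing subjects are counted as responders. The uncorrected chi-square is 120(a−b)² / [(a+b)(120−a−b)]. I assume 12 missing per arm (20%; the documents give no dropout rate), all nonresponders at the start.

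| a vs b | Conversions (rux, ana) | Chi-square | p |
|---|---|---|---|
| 18 vs 3 | 0, 0 | 12.99 | 0.0003 |
| 18 vs 9 | 0, 6 | 3.87 | 0.049 |
| 18 vs 10 | 0, 7 | 2.98 | 0.084 |
| 22 vs 12 | 4, 9 | 4.10 | 0.043 |
| 22 vs 13 | 4, 10 | 3.27 | 0.071 |
| 16 vs 4 | 0, 0 | 8.64 | 0.003 |
| 16 vs 7 | 0, 3 | 4.36 | 0.037 |
| 16 vs 8 | 0, 4 | 3.33 | 0.068 |

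The planned test is stratified over 2·2·2 = 8 strata. At 18 vs 9, with assumed stratum sizes and responders spread at random, the CMH p-value ranged from 0.044 to 0.056 (5th to 95th percentile). The rule for spreading conversions can therefore decide the result near the boundary.

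**4. Is the direction of error known?** An illustrative large-sample simulation (60,000 per arm) says no. Assumptions: baseline platelets 650·exp|N(0, 0.35)| and WBC 11·exp|N(0, 0.25)|; log counts fall as a subject effect times 1 − exp(−week/τ), with effect SDs 0.30 and 0.25 and visit noise SD 0.12; effects set so that 30% and 5% meet the 6-of-7 rule. Rates are for ruxolitinib stoppers.

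| Reason for stopping | τ (weeks) | True | Last-count model |
|---|---|---|---|
| At random, Weeks 2–31, 20% per arm | 2 / 4 / 8 / 12 | 31.0 / 29.8 / 29.8 / 30.1% | 28.5 / 24.2 / 18.2 / 13.5% |
| Uncontrolled counts at two successive visits, Weeks 12–28 | 2 / 4 / 8 / 12 | 2 / 2.5 / 5 / 9% | 12 / 12 / 10 / 8% |

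These use on-treatment last counts. Under random stopping the model understates; under lack-of-efficacy stopping it mostly overstates. If the last count in random stoppers is instead off drug, the imputed rate falls to 2.8–5.7% with half return to baseline and 0.4–0.5% with full return.

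**The case against.** **The consequence is limited.** The analysis is conditional and outside the alpha hierarchy, and nonresponder handling in 7.2.1 already gives one scenario that does not assume missing at random. This stands. A reader might infer that the primary comparison is in doubt; 7.2.1 does not use the imputation, so it is not.

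**Off-drug and open-label counts are a worst-case reading.** Protocol 6.6 asks only for reasonable efforts to hold the follow-up visit and allows a telephone contact, so some stoppers' last count will be at end of treatment. SAP 5.2 summarizes crossover data separately. This stands in part: the SAP does not prescribe such counts. But it does not exclude them, and 5.2 concerns summaries rather than imputation predictors.

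**The last count is informative.** Protocol 1.2.3.3 reports that 48.7% of ET subjects in the sponsor's earlier study withdrew, with lack of response and adverse events the leading reasons (17.9% each), though over a much longer exposure. A late on-treatment count helps identify subjects who are failing. This stands, and it rules out a tempting remedy, replacing the last counts with a Day 15 count for everyone. Protocol 5.4.1 permits dose increases for inadequate efficacy only after 2 weeks, so Day 15 largely precedes titration. In the lack-of-efficacy simulation a Day 15 model imputed 17–28% for ruxolitinib stoppers against a true 2–9%, further off than the last-count model in every case and in ruxolitinib's favor.

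**The table list is incomplete in the copy reviewed.** Titles 2.1.1–2.1.12 are not visible. The statement that no tipping-point analysis is specified rests on the methods text of SAP 7.2.3.1 and its subsections.

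**Conclusion.** The point holds as a defect in the one specified missing-data check. The mismatch in event windows is explicit in the SAP; the unrestricted last counts follow from its silence set against the protocol's visit schedule. The imputed rates for early stoppers can be wrong even if stopping is unrelated to outcome.

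The documents do not support a stronger statement that the check is biased against ruxolitinib by a given amount. Size and sign depend on how fast counts fall and why subjects stop, which the documents do not give; the simulated percentages show only that both directions are possible.

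On the assumed 12 missing per arm and the unstratified test, a planned-size result survives anything short of 7 of 12 anagrelide conversions against none on ruxolitinib. A weaker but still clearly significant result is lost at 4. That is the information a reader would need and the specified analysis does not give. The correction should be made, but it does not threaten the primary test.

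**What to change.** 1. In SAP 7.2.3.1.3, limit the last platelet, WBC and hemoglobin values to blinded on-treatment assessments: none after the last blinded dose and none from open-label treatment. State that a timing difference remains for early stoppers.
2. Drop infection and trauma/surgery from the imputation model, or define them over the same window for all subjects. Dropping them also thins a nine-effect model that, at 20% missing, would have about 0.8·(18 + 3) = 17 responders to fit.
3. In SAP 7.2.3.1.4, keep the imputation and add an arm-by-arm tipping-point table. Count from none to all of the missing-status subjects as responders in each arm, report the stratified CMH p-value for each pair, and state beforehand how conversions are spread across strata. Let this table carry the robustness conclusion.
4. Do not substitute a model based on Day 15 counts alone.
5. Clerical, at the same time: in Appendix E the outcome `Resp` is absent from the `VAR` list, and the analysis step models `Respo`.

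The cost is SAP wording and modest programming, with no new data. The robustness result may look less favorable than the imputation alone would suggest.

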### 7.2.3.1.2. Missing Data Display

For subjects discontinued before Week 32, the primary endpoint status will be missing. The number and percentage of subjects discontinued before Week 32 as well as the primary reasons for treatment discontinuation will be tabulated by treatment group.

For subjects in the study on or after Week 32 but with primary endpoint status missing as described in Section 7.2.3.1.1, the number of visits with nonmissing assessments of platelet counts and WBC counts between Weeks 32 and 52, as well as the number of visits where platelet counts are  $< 600 \times 10^9/L$  and WBC counts are  $< 10 \times 10^9/L$  will be tabulated by treatment group.

### 7.2.3.1.3. Covariates

Based on the clinical judgment ([Daly 2011](#), [Carel and Eviatar 1985](#)), the following covariates that may be related to the primary endpoint status will be considered:

- JAK2V617F mutation status at baseline: positive versus negative.
- Prior anagrelide use at baseline: yes versus no.
- Platelet count at baseline:  $\geq 1000 \times 10^9/L$  versus  $< 1000 \times 10^9/L$ .
- Last nonmissing assessment of platelet counts.
- Last nonmissing assessment of WBC counts.
- Last nonmissing assessment of hemoglobin.
- Any infection: yes versus no.
  - For subjects discontinued from the treatment before Week 32, any infection in the study period is considered; for subjects still in the study after Week 32, any infection after Week 32 is considered.
- Any trauma or surgery: yes versus no.
  - For subjects discontinued from the treatment before Week 32, any trauma or surgery in the study period is considered; for subjects still in the study after Week 32, any trauma or surgery after Week 32 is considered.

The covariates will be assessed based on data availability.

### 7.2.3.1.4. Multiple Imputation

For each missing value of the primary endpoint status, a list of  $m$  ( $m = 5$ ) imputed values will be generated through multiple imputation method and replaced for the missing value. The primary endpoint status is a dichotomous variable with values of responder and nonresponder; thus, logistic regression imputation method will be used to impute missing values of the primary endpoint status. In the logistic regression imputation method, a logistic regression model is fitted for the primary endpoint status variable with a set of covariates constructed from the effects, where the set of covariates is listed in Section 7.2.3.1.3 plus treatment group. The sample SAS code for multiple imputation is included in [Appendix E](#).

After multiple imputation,  $m$  imputed complete datasets will be generated. For each of  $m$  imputed datasets, the proportion of subjects who achieve primary endpoint will be summarized by treatment group. The combined results from  $m$  imputed data on proportion of subjects who achieve the primary endpoint will also be summarized, where the combined proportion is the average of the estimated proportion from each of  $m$  imputed datasets.

For each of  $m$  imputed datasets, a logistic regression model will be fitted for the primary endpoint status variable with treatment group, JAK2V617F mutation status, screening platelet count ( $\geq 1000 \times 10^9/L$  or  $< 1000 \times 10^9/L$ ), and prior anagrelide use (yes vs no) as covariates.

Additional multiple imputation methods may be explored to assist assessing the robustness of the primary endpoint due to missing value.

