### **3.1. Randomization**

This study will enroll approximately 120 subjects stratified by JAK2V617F mutation status (positive vs negative), platelet count ( $\geq 1000 \times 10^9/L$  or  $< 1000 \times 10^9/L$ ), and prior anagrelide use (yes vs no) at screening. Subjects will be randomized 1:1 to the following 2 treatment groups:

- Group A: ruxolitinib at a dose of 10 mg BID orally and anagrelide-placebo.
- Group B: anagrelide at a dose of 1 mg BID orally and ruxolitinib-placebo.

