### **3.2. Control of Type I Error**

The level of significance for the primary endpoint is 2-sided 0.05. The family wise alpha level will be controlled at 0.05 and will be controlled using a fixed sequential testing procedure. The proportion of subjects who achieve CR or PR at Week 32, as defined by ELN 2013 response criteria, will only be formally tested if the hypothesis for the primary endpoint is rejected. No other efficacy endpoints will be included in the alpha control.

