### **3.3. Sample Size Considerations**

Based on a literature search, the Incyte Phase 2 study (INCB 18424-256), and a difference in response rate of 25% (30% vs 5%), a total of approximately 120 subjects (60 subjects per group) would provide about 90% power to detect a treatment difference of 25% in the primary endpoint at 2-sided chi-square test with an alpha level of 0.05.

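### The planned multiple-imputation check of the primary endpoint has no safeguard against separation; with only 2 to 3 anagrelide responders expected, it can make a sound result look fragile

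*SAP*

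**What the plan says.** SAP 7.2.3.1 makes the missing-data analysis conditional: it runs only if more than 10% of subjects have missing primary endpoint status. Under 7.2.3.1.1, everyone who stops treatment before Week 32 counts as missing, as does anyone later whose status cannot be determined.

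SAP 7.2.3.1.4 then states that "logistic regression imputation method will be used to impute missing values of the primary endpoint status". The predictors are treatment and the 8 covariates of 7.2.3.1.3, among them "Last nonmissing assessment of platelet counts" and the matching WBC item. In each of 5 completed datasets, "a logistic regression model will be fitted for the primary endpoint status variable with treatment group" and the 3 stratification factors. Appendix E fits both steps by standard logistic procedures and pools the coefficients with PROC MIANALYZE.

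No penalised, augmented or exact method is named, and no reduced model or fallback. The nearest text says that covariates depend on data availability and that further imputation methods may be explored.

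The primary test is separate: a stratified CMH test in the ITT population, with subjects who discontinue without meeting the criteria counted as nonresponders (SAP 7.2.1).

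**The concern.** Ordinary maximum-likelihood logistic regression has no finite solution when a group contains no responders, or when a combination of predictors divides responders from nonresponders perfectly. The planned anagrelide response rate is so low that this is a realistic event.

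It does harm at two steps. In the imputation step, the treatment coefficient is drawn from a distribution with an enormous variance. Missing anagrelide subjects may then nearly all become responders in one completed dataset and none in the next. In the analysis step, a completed dataset with no anagrelide responder gives a huge standard error, and pooling carries it into the final result.

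The last platelet and WBC counts add to the risk, because the same two measurements make up the endpoint.

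This is the only missing-data model that the SAP specifies for the primary endpoint. It fails most often when the control arm has the fewest responders, which is when the treatment difference is largest.

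**Working it through.** **Inputs from the documents.** SAP 3.2: "The level of significance for the primary endpoint is 2-sided 0.05". SAP 3.3: 30% vs 5%, 60 per arm, a size that "would provide about 90% power to detect a treatment difference of 25" percentage points. SAP 3.1: 1:1 allocation. SAP 7.2.3.1.4: m = 5.

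**The plan's own figure.** Normal-approximation power for 60 per arm:
- standard error under no difference: sqrt(2 × 0.175 × 0.825 / 60) = 0.0694
- standard error under the alternative: sqrt((0.30 × 0.70 + 0.05 × 0.95) / 60) = 0.0655
- z = (0.25 − 1.96 × 0.0694) / 0.0655 = 1.74, so power is 95.9%

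The stated 90% is therefore conservative. If 20% dropouts count as nonresponders (24% vs 4%), power is 89.4%. None of this affects the point.

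**Model size.** Imputation: 8 covariates + treatment + intercept = 10 parameters. Analysis: treatment + 3 factors + intercept = 5.

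**Expected responders with known status** (missing rates are assumptions):

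| Missing | Ruxolitinib | Anagrelide | P(no anagrelide responder) |
|---|---|---|---|
| 10% | 54 × 0.30 = 16.2 | 54 × 0.05 = 2.7 | 0.95^54 = 6.3% |
| 20% | 48 × 0.30 = 14.4 | 48 × 0.05 = 2.4 | 0.95^48 = 8.5% |
| 30% | 42 × 0.30 = 12.6 | 42 × 0.05 = 2.1 | 0.95^42 = 11.6% |

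A lower control rate makes this worse. At 20% missing the chance is 0.97^48 = 23% for a 3% rate and 0.98^48 = 38% for a 2% rate. Such rates are plausible: Protocol 1.1 and 1.4 describe little effect of anagrelide on WBC, entry requires WBC of at least 11, and response requires less than 10.

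**What one empty cell does.** For 18/60 vs 0/60, the chi-square p is 0.000004. The logistic Wald p is 0.999, with a standard error of about 12,700. If only one of the 5 datasets looks like this, the pooled standard error is at least 12,700 / sqrt(5), or about 5,700.

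**Simulation.** Setup: 30% vs 5%, 60 per arm, missingness completely at random and equal by arm, 1,000 to 2,000 trials per setting. The primary test was the stratified CMH with missing counted as nonresponse. Assumed prevalences: JAK2 55%; prior anagrelide, platelets ≥1000 and infection 30% each; trauma 10%. The last platelet and WBC counts differed between responders and nonresponders by 0, 1 or 2 SD.

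Share of primary-significant trials in which the imputation analysis was not significant:

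| Method | Missing | 0 SD | 1 SD | 2 SD |
|---|---|---|---|---|
| As planned | 12% | 9% | 10% | 31% |
| As planned | 20% | 17% | 17% | 51% |
| As planned | 30% | 30% | 30% | 69% |
| Firth at both steps, m = 20 | 20% | 5% | 5% | 4% |
| Firth imputation, then stratified CMH | 20% | 3% | 2% | 2% |

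Further results at 20% missing:
- Separation in the imputation fit occurred in 26%, 28% and 68% of trials (0, 1, 2 SD).
- The completed anagrelide rate averaged 6.7%, 6.6% and 10.6% against a true 5%, and the ruxolitinib rate 30.5%, 30.5% and 32.6%. The mean difference was therefore 23.8, 23.9 and 22.0 points instead of 25.
- With no observed anagrelide responder, the planned method lost significance in 90-99% of true-positive trials, against 3-5% with Firth. At 0 SD these trials were 8.6% of the total and gave 0.086 × 0.987 = 8.5 of the 17 points lost.
- Cutting the imputation model to 5 parameters still lost 16%. Using m = 50 still lost 15% and 13% (0 and 1 SD).
- Stopping the fit after 8 iterations gave 17%, 19% and 28%.

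Other simulations with different covariate assumptions gave 10-27% at 7 missing per arm (about 12%), and 15-51% at 12 per arm (20%). With m = 5, one run gave 10-20% and 17-43% at 12% and 20% missing, against 1-5% and 7-11% with Firth.

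**The case against.** The strongest reply is that the analysis is secondary and conditional. The decision rests on the CMH test, and no SAP rule lets the imputation result displace it. The error shown runs toward no difference, so no false-positive risk arises from it. A p-value near 1 with a standard error in the thousands is visibly a fitting failure, and a competent analyst would notice. The SAP also reports the response proportions averaged across imputations, which separation in the analysis step cannot break. It tabulates early discontinuations, allows other imputation methods, and labels its code as a sample.

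Most of this stands, and it limits the severity. Two parts do not answer the point. Permission to explore other methods is not a prespecified safeguard: a remedy chosen after the planned analysis has failed invites doubt about why it was chosen. And the failure is not always visible. At 1 SD and 20% missing, trials with 1, 2, or 3 or more observed anagrelide responders still lost significance 7-10% of the time, and at 2 SD 40-57% of the time.

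It is also fair to say that the percentages depend on the model. They move with the assumed strength of the last counts and with how the software handles separation.

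**Conclusion.** The point holds: the plan lacks a separation safeguard in a conditional sensitivity analysis. As written, that analysis contradicts a significant primary result in roughly 10-30% of trials at about 12% missing and 17-50% at about 20% missing, even when missingness is harmless. These ranges assume 30% vs 5%, 60 per arm and missingness completely at random. The direction was the same in every setting tried; the exact sizes are less certain.

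Two stronger readings are tempting but not supported. A reader might infer that the check can overturn the primary result. It cannot, because SAP 3.2, 7.1 and 7.2.1 rest the decision on the CMH test. It can only make that result look fragile.

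A reader might also infer that the cause is 10 parameters fitted to about 17 responders. The documents do not give that count, which needs about 20% missing, and only the imputation model has 10 parameters. A main driver is the sparse anagrelide arm combined with unpenalised Wald inference. The extra covariates matter most if the last platelet and WBC counts predict response strongly.

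This should be changed before unblinding, but it does not threaten the primary analysis.

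**What to change.** Amend SAP 7.2.3.1.4 and Appendix E in two places.

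1. Imputation step: prespecify a penalised (Firth) or augmented logistic model for responder status.
2. Analysis step: replace the ordinary logistic model in each dataset by a penalised logistic model, or by the stratified CMH test or the stratum-adjusted rate difference. State the rule for pooling across imputations.

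The CMH or rate-difference option also keeps the check closer to the primary analysis. More imputations help, but not on their own.

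Imputing the Week 32-52 platelet and WBC counts and deriving status from them is an optional alternative. It needs a model for up to 11 visits × 2 counts per subject, so it has sparse-data questions of its own.

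The cost is SAP wording, some reprogramming and slight shrinkage of the estimates. No new data or subjects are needed.
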